### 8.3. Data Sources

Patients with PsA will be identified in the rheumatology registry. Patient demographic information (age, gender), education level (years), present smoking status, disease duration (years), current MTX and steroid therapy (yes/no), baseline DAPSA (Disease Activity in Psoriatic Arthritis), anti-citrullinated protein antibody (ACCP) status will be obtained. Primary Outcomes: DAPSA in first and last follow up visit.

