#### **8.6. Data Analysis**

Categorical covariates will be described by frequency distribution while continuous covariates expressed in terms of their mean and standard deviation or median and interquartile range as appropriate. Patients will be divided for sero-positive PsA and sero-negative PsA (according to ACCP status) the unadjusted comparisons between groups of the covariates and the outcomes are evaluated using chi tests for categorical data, while for continuous data, we used the student's t-test for normally distributed variables and the Kruskall-Wallis test for non-parametric data.

We determined the effect of sero-positive on the biologic treatment response patients with PsA a multivariate analysis by using a stepwise linear regression model. The response variable is defined as disease activity index (either DAPSA, DAS-28 ESR, or DAS-28 CRP) at last visit. The baseline variables considered demographic data, disease duration (years), methotrexate (yes/no), current steroid therapy (yes/no), baseline disease activity index, anti-CCP (yes/no), psoriasis presentation and present smoking (yes/no).

We determined the effect of response by using change from baseline in disease activity index at the last visit. P value <0.05 is considered statistically significant, without multiplicity adjustment, for this post-hoc analysis.

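### Section 8.6 measures response both as last-visit score and as change from baseline, fixes the role of baseline in neither, and names no primary analysis, so the ACCP contrasts can differ

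*Combined protocol and SAP*

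**What the plan says.** Section 8.6 (Data Analysis) contains three routes to an ACCP effect.

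- **Regression of the last-visit score.** "The response variable is defined as disease activity index (either DAPSA, DAS-28 ESR, or DAS-28 CRP) at last visit". The method is "a multivariate analysis by using a stepwise linear regression model". The variables to be considered include "baseline disease activity index, anti-CCP (yes/no), psoriasis presentation and present smoking (yes/no"). Nothing says that baseline, or ACCP itself, stays in the model whatever the selection finds.
- **Change from baseline.** The next paragraph says: "We determined the effect of response by using change from baseline in disease activity index at the last visit". No model, covariate list or adjustment is attached to that sentence.
- **Unadjusted group comparisons.** Earlier in the section, "the unadjusted comparisons between groups of the covariates and the outcomes are evaluated using chi"-squared tests, with t or Kruskal-Wallis tests for continuous data.

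The testing rule is "P value <0.05 is considered statistically significant, without multiplicity adjustment, for this post-hoc analysis". None of the three routes is called primary.

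Section 8.3 (Data Sources) gives a further wording: "Primary Outcomes: DAPSA in first and last follow up visit". It does not say how the two visits are combined, or whether the first one is the pre-treatment visit. The same section lists baseline DAPSA separately among the data to be obtained.

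**The concern.** The groups are formed by ACCP status, so nothing balances baseline DAPSA between them. Section 6 describes ACCP as a marker of poor prognosis, which makes a baseline difference plausible, although the plan gives no size for it.

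If baseline differs, the three routes do not estimate the same quantity. Suppose ACCP has no effect given baseline. The group that starts higher will then tend to finish higher, which looks like a worse response on the last-visit score. It will also tend to fall further, which looks like a better response on raw change. The study asks one question, whether ACCP status affects response to etanercept. A plan that allows each of these results to be tested at 0.05 and does not rank them lets the answer depend on which one is quoted.

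**Working it through.** The plan gives no sample size, effect size, standard deviation or expected imbalance, so it has no figure to reproduce. The check is algebra, with assumed inputs where numbers are needed.

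**Notation.** D is the baseline mean difference (ACCP-positive minus ACCP-negative), L the last-visit mean difference, and b the within-group slope of last-visit score on baseline.

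**Contrasts.**
- Unadjusted last visit: L
- Unadjusted change: L − D
- Baseline-adjusted last visit: L − b·D
- Change modelled with baseline as covariate: also L − b·D, because subtracting baseline from the outcome alters only the baseline coefficient

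**Gaps.**
- Both unadjusted: L − (L − D) = D
- Adjusted last visit against unadjusted change: (L − b·D) − (L − D) = (1−b)·D
- Both modelled with baseline and the same covariates: 0

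**Numbers for an assumed D of 6 points, with no ACCP effect given baseline (so L = b·D).**

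| b (assumed) | Unadjusted last visit, b·D | Unadjusted change, −(1−b)·D | Gap, both unadjusted | Gap, adjusted last visit vs unadjusted change |
|---|---|---|---|---|
| 0.3 | +1.8 | −4.2 | 6.0 | 4.2 |
| 0.5 | +3.0 | −3.0 | 6.0 | 3.0 |
| 0.7 | +4.2 | −1.8 | 6.0 | 1.8 |

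**Check on simulated data** (assumed: 30 ACCP-positive, 200 ACCP-negative, baseline SD 12, residual SD 8, imbalance 5, b = 0.5). In one data set D = 5.437, the unadjusted last-visit contrast was 1.431 and the unadjusted change contrast −4.006; their gap is 1.431 + 4.006 = 5.437 = D. The baseline-adjusted contrast was −1.258 whether the outcome was last visit or change. Its gap from unadjusted change is −1.258 + 4.006 = 2.748, which agrees with (1 − 0.495) × 5.437 to rounding, where 0.495 is the fitted slope.

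**Share of tests with P < 0.05** under the same group sizes and SDs, imbalance 5, no ACCP effect given baseline, 4,000 simulations per slope:

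| b | Unadjusted change | Unadjusted last visit | Baseline forced in |
|---|---|---|---|
| 0.3 | 33% | 15% | 5% |
| 0.5 | 24% | 25% | 5% |
| 0.7 | 13% | 34% | 5% |

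**How often selection would drop baseline.** The plan states no entry rule. Assuming retention at P < 0.05 on the baseline–outcome correlation alone, the simulated share of samples in which baseline is not kept is:

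| Correlation r | N = 60 (assumed) | N = 100 (assumed) |
|---|---|---|
| 0.3 | 35% | 14% |
| 0.4 | 10% | 1.4% |
| 0.5 | 1.4% | 0.1% |
| 0.7 | about 0% | about 0% |

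With similar SDs at both visits, r and b are about equal. The correlations at which baseline is often dropped are therefore those at which b·D, the distortion in the last-visit contrast, is small: about 0.2 × 6 = 1.2 points at b = 0.2.

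**The case against.** Four arguments count against pressing this point too hard.

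1. **The gap is not always D.** A reader might infer that the two definitions must differ by exactly the baseline imbalance. That holds only when both contrasts are unadjusted. The last-visit analysis in 8.6 is a regression with baseline among its candidates; once baseline is kept, the gap from unadjusted change is (1−b)·D. This stands. The full gap D can still arise, because 8.6 also plans unadjusted comparisons of the outcomes.

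2. **The plan does not call the change analysis unadjusted.** The sentence follows the covariate list and could mean that change is modelled with the same covariates, in which case the ACCP coefficients coincide. This stands too. The supportable defect is that the model for change is not specified.

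3. **Stepwise selection will usually keep a strong baseline.** A reader might infer that baseline is likely to be lost. The retention figures do not support this beyond weak correlations and small samples. The risk remains open only because the plan gives no study size and no rule that keeps baseline.

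4. **Baseline adjustment is not automatically right in non-randomised groups.** This is Lord's paradox. If the ACCP groups have stable, different underlying means and baseline is measured with error, each group regresses to its own mean. In a simulation with true-score SD 8, error SD 8, a stable difference of 6 and equal change in both groups, the change contrast was 0.0 and the baseline-adjusted contrast +3.0. This stands: adjustment removes the imbalance bias only if the groups share one regression line given observed baseline, and the documents do not settle that. It is a reason to keep change as a labelled sensitivity analysis. It does not justify leaving the choice open.

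**Conclusion.** The point holds in this form: 8.6 uses two measures of response, gives a model for only one, leaves baseline and ACCP as optional terms in that model, adds unadjusted comparisons, and names no primary analysis. Depending on what is fitted, the ACCP contrasts can differ by D, by (1−b)·D, or not at all, and the two unadjusted contrasts can have opposite signs.

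For an assumed imbalance of 6 points, the difference between an adjusted last-visit result and an unadjusted change result is 4.2 to 1.8 points over slopes of 0.3 to 0.7. D, b, the SDs, the group sizes and the retention rule are all assumptions. The documents establish that the contrasts can diverge; they do not establish that they did, or by how much.

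**What to change.** In 8.6, name one primary analysis: last-visit DAPSA regressed on ACCP status, with baseline DAPSA and ACCP both forced into the model, reporting the adjusted ACCP difference with its 95% CI. State that this estimate assumes one regression line on observed baseline for both groups.

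Report change from baseline in one of three stated ways: descriptively, from the same baseline-adjusted model, or as a labelled sensitivity analysis to the common-line assumption. Say that the unadjusted comparisons of outcomes are descriptive.

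In 8.3, replace first and last follow-up visit with baseline and last visit, and say which visit supplies the baseline value.

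No new data are needed, since baseline DAPSA is already among the variables obtained. Section 5 records the final study report as complete on 29 June 2021, so the cost is revised wording plus a rerun and updated reporting on data already collected.

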**PFIZER CONFIDENTIAL**

## 6. RATIONALE AND BACKGROUND

Psoriatic arthritis is a chronic, systemic inflammatory arthritis that occurs in 6 to 42% of patients with psoriasis, affecting the peripheral joints, tendons, ligaments, and the axial skeleton. Current treatment guidelines for psoriatic arthritis recommends conventional synthetic disease-modifying antirheumatic drugs (DMARDs), such as methotrexate, as initial therapy, followed by biologic DMARDs (tumor necrosis factor [TNF] inhibitors, interleukin- 12 and interleukin-23 inhibitors, and interleukin-17 inhibitors) or apremilast in patients who had an inadequate response to conventional synthetic DMARDs.

The presence of anti-CCP antibodies in PsA and the prevalence was between 5.6 and 15.7% giving the optionality of biological treatment for RA patients, identifying a predictor for response will acquire more attention to rheumatologists for such patients.

Psoriatic arthritis is a severe form of arthritis in which deformities and joint damage develop in many patients. Bone erosions are observed in 47% of patients within the first 2 years, despite the use of traditional disease-modifying medications in more than half the patients. Furthermore, presence of ACCP in PsA patients consider one of bad prognostic factors for PsA Patients.

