## 8. RESEARCH METHODS

### 8.1. Study Design

- **Retrospective analysis** of patients with PsA that received etanercept from Baghdad Teaching Hospital (Rheumatology Center) from May 2012 until August 2019 (inclusion and exclusion criteria will apply for selecting patients).
- **Primary objective:** Determine the clinical impact of ACCP positivity for management (etanercept) in patients with PsA compared to negative ACCP patients.
- **Primary objective:** Determine the clinical impact of ACCP positivity for management (etanercept) in patients with PsA compared to negative ACCP patients.

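### Section 8.6 applies an unadjusted P<0.05 to every test, so the study's single ACCP question is tested several ways with no one test named as the answer

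*Combined protocol and SAP*

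**What the plan says.** The primary objective in Section 8.1 is a single contrast: "Determine the clinical impact of ACCP positivity for management (etanercept) in patients with PsA compared to negative ACCP patients". The research question in Section 7 and the hypothesis in Section 8.2 also concern ACCP status only.

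Section 8.6 of the combined protocol and SAP plans more than one test of that contrast:

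- Unadjusted comparisons of the outcomes between the two ACCP groups. Section 8.3 gives the primary outcome as DAPSA at the first and last follow-up visits.
- An adjusted analysis, described as "a multivariate analysis by using a stepwise linear regression model". Its outcome is left open: "The response variable is defined as disease activity index (either DAPSA, DAS-28 ESR, or DAS-28 CRP) at last visit".
- An analysis of change from baseline to the last visit.

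Anti-CCP enters the stepwise model as one item in a list: "The baseline variables considered demographic data, disease duration (years), methotrexate (yes/no), current steroid therapy (yes/no), baseline disease activity index, anti-CCP (yes/no), psoriasis presentation", followed by smoking. The significance rule then covers everything: "P value <0.05 is considered statistically significant, without multiplicity adjustment, for this post-hoc analysis". It is not limited to the ACCP coefficient, and no sentence says how the other P values are to be read.

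**The concern.** A 5% level describes one test. Where one question is tested in several ways and none is named as the answer, any of them can be cited as the ACCP result, and the chance of a false one exceeds 5%. A reader of the report could not tell which P value was meant to settle the question.

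A second, smaller matter concerns the model. A stepwise procedure screens all candidates by the same rule and returns those it keeps. Anti-CCP has no reserved place, so the final model could omit it and still show other terms as significant. The plan does not say that those terms are there for adjustment only.

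**Working it through.** The documents state no sample size, power or family-wise error rate, so there is no figure of the plan's own to reproduce.

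**1. ACCP tests on one index**

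Inputs from the documents: a level of 0.05 per test without adjustment (Section 8.6), and three ACCP tests at the last visit (unadjusted value, change from baseline, adjusted value). The change-from-baseline sentence does not spell out a group comparison; I count it as a test.

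Assumed: N = 100 or 200, 10% ACCP-positive, correlation r = 0.4–0.6 between visits, equal variances, and no ACCP difference at any visit.

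If the three tests were independent, the chance of at least one false positive would be 1 − 0.95³ = 14.3%. They share data, so the figure is lower. With equal variances the estimates correlate approximately as follows:

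| Pair | Formula | r = 0.4 | r = 0.5 | r = 0.6 |
|---|---|---|---|---|
| last visit, change | √((1 − r)/2) | 0.55 | 0.50 | 0.45 |
| last visit, adjusted | √(1 − r²) | 0.92 | 0.87 | 0.80 |
| change, adjusted | √((1 + r)/2) | 0.84 | 0.87 | 0.89 |

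Simulation with t-tests and a linear model containing baseline and seven null covariates gives:

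- three tests: about 9–11%;
- four tests, if the first visit in Section 8.3 is a separate follow-up comparison: about 13–15% (independence would give 1 − 0.95⁴ = 18.5%).

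**2. More than one index**

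Taking the adjusted stepwise model alone, running it on all three indices and counting any ACCP hit gives about 11% instead of 5% (assumed n = 150, residual correlation 0.8 between indices). This comes on top of the several tests per index in step 1; I have not combined the two.

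**3. Do the covariates inflate the ACCP test?**

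No. Stepwise selection was simulated with n = 80, 150 and 300, entry at 0.05, removal at 0.10, covariate correlation 0 or 0.3, baseline truly prognostic, and 7 or 8 null covariates. The thresholds are assumed, since the plan gives none. The ACCP false-positive rate was 4–6%.

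**4. Covariates, if they were read as findings**

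Section 8.6 says only demographic data. Section 8.3 gives the content: "Patient demographic information (age, gender), education level (years), present smoking status, disease duration (years". Taking age and gender, and adding disease duration, methotrexate, steroid, psoriasis presentation and smoking, there are seven terms besides ACCP and the baseline index. With education there are eight. Each is counted as one coefficient.

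| Truly null terms, k | 1 − 0.95ᵏ |
|---|---|
| 3 | 14.3% |
| 5 | 22.6% |
| 7 | 30.2% |
| 8 | 33.7% |

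The stepwise simulation gave 29–31% for seven null terms and 31–35% for eight, so neither selection nor moderate correlation changes the figure much.

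**The case against.** The strongest defence is that the plan is open about this. It says "without multiplicity adjustment, for this post-hoc analysis", and unadjusted P values are common in a disclosed post-hoc observational analysis. Adjustment covariates normally need no multiplicity correction, and here they leave the ACCP test at about 5%. The final study report is dated 29 June 2021 (Section 5), so a change now can affect only how results are presented and read.

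Most of this stands. Disclosure, however, does not tell the reader which of several ACCP tests answers the question. The argument about covariates presumes a prespecified model with a designated term of interest, and a stepwise search over a list that includes anti-CCP is not such a model.

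A reader might go further and infer that about 3 analyses in 10 would report a false predictor of response. The documents do not support this. No section plans to report covariates as predictors, and Section 8.6 gives the model's purpose as the effect of seropositivity. The rationale does speak of "identifying a predictor for response will acquire more attention to rheumatologists for such patients", but in a sentence about anti-CCP antibodies, so the natural reading is that ACCP is the predictor. The 30% also requires all seven terms to be truly null, which nothing in the documents establishes. Pooling ACCP tests and covariates into one larger error rate would need the same reading and the same assumption.

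**Conclusion.** The point holds as a modest one. The objective is a single contrast, but Section 8.6 tests it several ways at an unadjusted 0.05 and names none of them as the test. On one index, the chance of at least one false ACCP result is about 9–11%, or about 13–15% with a separate first follow-up test, and more if several indices are run. The size depends on the assumed N, ACCP prevalence and visit correlation, and on no ACCP difference at any visit.

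The covariates do not damage the ACCP test. Their part is conditional: if retained terms were read as findings and all seven were null, about 30% of analyses could name at least one false predictor, or 14–23% if only three to five were null. This does not make the ACCP comparison invalid. It is a gap in stating what is tested, and it is cheap to close.

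**What to change.** Make two changes in Section 8.6. Both are needed: stepwise selection itself tests the covariates and may drop anti-CCP, which would leave no coefficient to test.

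1. Replace the stepwise sentence with a linear model of last-visit DAPSA in which anti-CCP, baseline DAPSA and the listed covariates are all entered without selection. State which variables count as demographic data.
2. Replace the P-value sentence with:

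> Statistical significance (two-sided P<0.05) is assessed for one test only, the anti-CCP coefficient in this model. Other terms are for adjustment and are not interpreted as predictors; all other comparisons, including change from baseline and other indices, are given as estimates with 95% confidence intervals without significance claims.

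DAPSA is the natural choice because Section 8.3 already names it as the primary outcome. With one named test the ACCP false-positive rate is 5%, whatever the number of adjustment terms.

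The cost is a rewritten paragraph and one refitted model. The report can no longer claim significance for secondary comparisons or covariates. Entering every term also uses at least nine coefficients besides the intercept (anti-CCP, baseline and seven others), which would widen the interval if the number of patients is small; Section 8.4 sets no study size. For results already reported, the same rule can be applied to how they are presented, labelled as decided after the analysis.

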#### **8.7. Quality Control**

Not Applicable (NA).

#### **8.8. Limitations of the Research Methods**

The missing data that could lead to bias is an identified limitation in this study.

#### **8.9. Other Aspects**

Not Applicable (NA).

### **9. PROTECTION OF HUMAN SUBJECTS**

#### **9.1. Patient Information**

This study involves data that exist in anonymized structured format and contain no patient personal information.

## **9.2. Patient Consent**

As this retrospective study involves anonymized structured data, which according to applicable legal requirements do not contain data subject to privacy laws, obtaining informed consent from patients by Pfizer is not required.

## **9.3. Institutional Review Board (IRB)/Independent Ethics Committee (IEC)**

Not required.

## **9.4. Ethical Conduct of the Study**

The study conducted in accordance with legal and regulatory requirements, as well as with scientific purpose, value and rigor and follow generally accepted research practices described in Guidelines for Good Pharmacoepidemiology Practices (GPP) issued by the International Society for Pharmacoepidemiology (ISPE), Good Epidemiological Practice (GEP) guidelines issued by the International Epidemiological Association (IEA), and Good Practices for Outcomes Research issued by the International Society for Pharmacoeconomics and Outcomes Research (ISPOR).

## **10. MANAGEMENT AND REPORTING OF ADVERSE EVENTS/ADVERSE REACTIONS**

This study involves data that exist as structured data by the time of study start. In these data sources, individual patient data are not retrieved or validated, and it is not possible to link (ie, identify a potential association between) a particular product and medical event for any individual. Thus, the minimum criteria for reporting an adverse event (AE) (ie, identifiable patient, identifiable reporter, a suspect product, and event) cannot be met.

[figure not shown]
[figure not shown]
## **11. PLANS FOR DISSEMINATING AND COMMUNICATING STUDY RESULTS**

In the event of any prohibition or restriction imposed (eg, clinical hold) by an applicable competent authority in any area of the world, or if the investigator is aware of any new information which might influence the evaluation of the benefits and risks of a Pfizer product, Pfizer should be informed immediately.

**13. LIST OF TABLES**

NA.

[figure not shown]
**14. LIST OF FIGURES**

NA.

**ANNEX 1. LIST OF STAND-ALONE DOCUMENTS**

None.

PFIZER CONFIDENTIAL

